5.2.1 Dose Selection/Modification

5.2.1.1 Dose Selection

The rationale for selection of doses to be used in this trial is provided in Section 4.0 - Background and Rationale.

The dose of pembrolizumab is fixed at 200 mg IV Q3W.

The dose escalation schema of trametinib is as follows. Each cycle is Q3W (21 days).

Table 3. Dose Escalation Schema for Trametinib

Dose Level	Trametinib dose (PO Daily) Q3W	Pembrolizumab (MK-3475) dose IV Q3W
-1	1.5 mg (D1-D7)	200 mg
*1	1.5 mg (D1-D10)	200 mg
2	2.0 mg (D1-D10)	200 mg

^{*} Dose level 1 is the starting dose. For each cohort, trametinib dose will be the same for lead in and for concurrent trametinib + pembrolizumab administration.

For Cohort A: Lead in trametinib will precede combination trametinib and pembrolizumab, which will commence for C2.

For Cohort B: Lead in pembrolizumab will precede combination trametinib and pembrolizumab, which will commence for C2.

The recommended dose expansion and recommended phase II dose (RP2D) will be determined by the overall assessment of the MTD (the maximum dose level where 6 patients have been treated in the dose escalation portion of the study) and toxicities observed in the dose escalation portion of this study.

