5.2.1.2 Dose Modification (Escalation/Titration/Other)

Adverse events (both non-serious and serious) associated with pembrolizumab exposure may represent an immunologic etiology. These adverse events may occur shortly after the first dose or several months after the last dose of treatment. Pembrolizumab must be withheld for drug-related toxicities and severe or life-threatening AEs as per Table 5 below. See dose modification and supportive care guideline sections, including use of corticosteroids. There are no dose reductions for pembrolizumab.

Dosing interruptions are permitted in the case of medical/surgical events or logistical reasons not related to study therapy (e.g., elective surgery, unrelated medical events, patient vacation, and/or holidays). Subjects should be placed back on study therapy within 3 weeks of the scheduled interruption. The reason for interruption should be documented in the patient's medical record.

Table 4. Dose Modification for Trametinib. Lowest permitted Trametinib dose will be 1.5 mg daily.

Dose Level	Trametinib Dose (QD) (D1-D10 administration unless otherwise specified)		
For Starting Dose	2 mg	1.5 mg	1.5 mg (dosed from D1-D7)
1 st Does Reduction	1.5 mg	1.5 mg (dosed from D1-D7)	Discontinue Trametinib
2 nd Dose Reduction	1.5 mg (dosed from D1-D7)	Discontinue trametinib	-

Table 5. Dose Modification Guidelines for Pembrolizumab (MK-3475) for Drug-Related Adverse Events

Toxicity	Hold Treatment For Grade	Timing for Restarting Treatment	Treatment Discontinuation
Diarrhea/Colitis	2-3	Toxicity resolves to Grade 0-1	Toxicity does not resolve within 12 weeks of last dose or inability to reduce corticosteroid to 10 mg or less of prednisone or equivalent per day within 12 weeks
	4	Permanently discontinue	Permanently discontinue
AST, ALT, or Increased	2	Toxicity resolves to Grade 0-1	Toxicity does not resolve within 12 weeks of last dose
Bilirubin	3-4	Permanently discontinue (see exception below) ^a	Permanently discontinue
Type 1 diabetes mellitus (if new onset) or	T1DM or 3-4	Hold pembrolizumab for new onset Type 1 diabetes mellitus or Grade 3-4 hyperglycemia	Resume pembrolizumab when patients are clinically and metabolically stable

Toxicity	Hold Treatment For Grade	Timing for Restarting Treatment	Treatment Discontinuation
Hyperglycemia		associated with evidence of beta cell failure	

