Grade 2 (Intolerable) or Grade 3	Interrupt therapy until toxicity is grade 0-1 and reduce by one dose level when resuming therapy.
Grade 4	Discontinue permanently, or interrupt therapy until Grade 0 to 1 and reduce by one dose level when resuming therapy.

Please follow Table 5 and Table 6 for dose modifications unless specified below.

For Grade \geq 3 drug related adverse events attributed to trametinib both pembrolizumab and trametinib should be simultaneously interrupted with the exceptions shown below.

Except for Grade ≥ 3 lymphopenia

Exceptions where dose modifications are necessary for only trametinib:

- LVEF reduction
- Retinal Vein Occlusion (RVO) and Retinal Pigment Epithelial Detachment (RPED)

Table 7. Trametinib Dose Modification Guidelines and Stopping Criteria for LVEF Decrease

Clinical Evaluation	LVEF-drop (%) or CTCAE grade	Action and Dose Modification
Asymptomatic	Absolute decrease of >10% in LVEF compared to baseline and ejection fraction below the institution's LLN.	 Interrupt trametinib and repeat ECHO/MUGA within 2 weeks.^a If the LVEF recovers within 4 weeks (defined as LVEF ≥LLN and absolute decrease ≤10% compared to baseline): Consult with the Novartis trametinib medical monitor and request approval for restart. Restart treatment with trametinib at reduced dose by one dose level. Repeat ECHO/MUGA 2, 4, 8, and 12 weeks after restart; continue in intervals of 12 weeks thereafter. If LVEF does not recover within 4 weeks: Consult with cardiologist. Permanently discontinue trametinib. Report as SAE Repeat ECHO after 2, 4, 8, 12, and 16 weeks or until resolution.
Symptomatic ^b	 Grade 3: resting LVEF 39-20% or >20% absolute reduction from baseline Grade 4: Resting LVEF ≤20%. 	 Permanently discontinue trametinib. Report as SAE. Consult with cardiologist. Repeat ECHO/MUGA after 2, 4, 8, 12, and 16 weeks or until resolution.

^a If ECHO/MUGA does not show LVEF recovery after 2 weeks, repeat ECHO/MUGA 2 weeks later.

^b Symptoms may include: dyspnea, orthopenea, and other signs and symptoms of pulmonary congestion and edema.

Table 8. Trametinib Withholding and Stopping Criteria for QTc Prolongation

Prolongation*	Action and Dose Modification

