Grade 1*	Consult ophthalmologist within 7 days of onset.	 If dilated fundus examination cannot be performed within 7 days of onset, hold trametinib until RPED and RVO can be excluded by retina specialist/ophthalmologist. If RPED and RVO excluded, continue/or restart trametinib at same dose level. If RPED suspected/diagnosed: See RPED dose modification table below (following this table); report as SAE. If RVO diagnosed: Permanently discontinue trametinib and report as SAE.
Grade 2 and Grade 3	Consult ophthalmologist immediately.	 Hold trametinib If RPED or RVO excluded, restart trametinib at same dose level after visual AE is ≤ grade 1. If no recovery within 3 weeks, discontinue trametinib If RPED diagnosed: See RPED dose modification table below; report as SAE. If RVO: Permanently discontinue trametinib and report as SAE.
Grade 4	 Consult ophthalmologist immediately. Report as SAE. 	 Hold Trametinib If RPED/RVO excluded, may restart trametinib at same or reduced dose after discussion with the Principal Investigator If RVO or RPED, permanently discontinue trametinib.

Abbreviations: RPED=retinal pigment epithelial detachments; RVO=retinal vein occlusion; SAE=serious adverse event

* If visual changes are clearly unrelated to study treatment (e.g., allergic conjunctivitis), monitor closely but ophthalmic examination is notrequired.

Table 11. Trametinib Dose Modification for RPED

Event CTCAE Grade	Action and Dose Modification
Grade 1 RPED (Asymptomatic; clinical or diagnostic observations only)	Continue treatment with retinal evaluation monthly until resolution. If RPED worsens, follow instructions below.
Grade 2-3 RPED (Symptomatic with mild to moderate decrease in visual acuity; limiting instrumental ADL)	 Interrupt trametinib. Retinal evaluation monthly. If improved to ≤ Grade 1, restart trametinib with one dose level reduction (reduced by 0.5 mg) or discontinue in patients taking trametinib 1 mg daily. If no recovery within 4 weeks permanently discontinue trametinib

Table 12. Management and Dose Modification Guidelines for Diarrhea

CTCAE Grade	Adverse Event Management	Action and Dose Modification

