Grade 1	 CT scan (high-resolution with lung windows) recommended. Work-up for infection. Monitoring of oxygenation via pulse- oximetry recommended. Consultation with pulmonologist recommended. 	Continue trametinib at current dose.
Grade 2	 CT scan (high-resolution with lung windows). Work-up for infection. Consult pulmonologist. Pulmonary function tests: If < normal, repeat every 8 weeks until ≥ normal. Bronchoscopy with biopsy and/or BAL recommended. Symptomatic therapy including corticosteroids if clinically indicated. 	 Interrupt trametinib and pembrolizumab until recovery to grade ≤1. If AE resolved to Grade ≤1 and relationship to trametinib and or pembrolizumab is equivocal, restarting pembrolizumab and trametinib (with dose reduction at investigators discretion) may be considered, after discussion with the study chair. If treatment delay is > 4 weeks, permanently discontinue trametinib and pembrolizumab.
Grade 3	 CT scan (high-resolution with lung windows). Work-up for infection. Consult pulmonologist. Pulmonary function tests-if < normal, repeat every 8 weeks until ≥ normal. Bronchoscopy with biopsy and/or BAL if possible. Symptomatic therapy including corticosteroids as clinically indicated. 	Permanently discontinue trametinib and pembrolizumab.
Grade 4	• Same as grade 3.	Permanently discontinue trametinib and pembrolizumab.

Dose Reduction Scheme for Trametinib

No dose reductions for trametinib are permitted below 1.5 mg PO daily.

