9.2 Trametinib

Trametinib tablets are provided as immediate release tablets for oral administration containing trametinib dimethyl sulfoxide (GSK1120212B) equivalent to 0.125 mg, 0.5 mg or 2 mg of trametinib. All formulation excipients are compendial and are commonly used in oral formulations. Refer to the trametinib Investigator's Brochure for a list of excipients.

The trametinib tablets are packaged in high-density polyethylene bottles with labels bearing the appropriate label text as required by governing regulatory agencies. All study drug will be dispensed in child-resistant packaging.

Refer to the Pharmacy Manual/site investigational product manual for additional guidance on study drug storage, preparation and handling.

Study drug labels will contain information to meet the applicable regulatory requirements.

Classification

Cytotoxic drug: molecular targeted cytotoxic drug

Mechanism of Action

Trametinib is a reversible inhibitor of mitogen-activated extracellular signal regulated kinase 1 256 (MEK1) and MEK2 activation and of MEK1 and MEK2 kinase activity. MEK proteins are 257 upstream regulators of the extracellular signal-related kinase (ERK) pathway, which promotes 258 cellular proliferation. BRAF V600E mutations result in constitutive activation of the BRAF 259 pathway which includes MEK1 and MEK2. Trametinib inhibits BRAF V600 mutation-positive 260 melanoma cell growth in vitro and in vivo.

Metabolism

Trametinib is metabolized predominantly via deacetylation alone or with mono282 oxygenation or in combination with glucuronidation biotransformation pathways in vitro. 283 Deacetylation is likely mediated by hydrolytic enzymes, such as carboxyl-esterases or amidases. 284 Following a single dose of [14C]-trametinib, approximately 50% of circulating radioactivity is 285 represented as the parent compound. However, based on metabolite profiling after repeat dosing 286 of trametinib, > 75% of drug-related material in plasma is the parent compound.

Contraindications

None.

Availability

Trametinib will be supplied by Novartis.

Storage and Handling

Trametinib tablets should be stored refrigerated at 2° to 8°C (36° to 46°F). Do not freeze. Dispense in original bottle. Do not remove desiccant. Protect from moisture and light. Do not place medication in pill boxes.

Side Effects

Complete and updated adverse event information is available in the Investigational Drug Brochure and/or product package insert.

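### Table 11's restart rule for Grade 2-3 retinal pigment epithelial detachment leads to 1.0 mg trametinib, below the protocol's 1.5 mg floor and off the Table 4 ladder

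*Combined protocol and SAP*

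**What the plan says.** Section 5.2.1.2 contains three instructions that bear on this case.

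- **Table 11 (RPED).** Trametinib is interrupted for Grade 2-3 RPED, which the table describes as symptomatic with reduced visual acuity. If the event improves to Grade 1 or less, the site is to "restart trametinib with one dose level reduction (reduced by 0.5 mg) or discontinue in patients taking trametinib 1 mg daily". Without recovery in 4 weeks, trametinib stops for good.
- **Table 4 (reduction ladder).** The steps run from 2 mg on days 1-10, to 1.5 mg on days 1-10, to 1.5 mg on days 1-7, to discontinuation. The table's title states: "Lowest permitted Trametinib dose will be 1.5 mg daily".
- **Dose Reduction Scheme for Trametinib (after Table 14).** The floor is repeated: "No dose reductions for trametinib are permitted below 1.5 mg PO daily".

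The text after Table 6 addresses precedence: "Please follow Table 5 and Table 6 for dose modifications unless specified below". In section 5.2.1.1, Table 3 lists 1.5 mg on days 1-7 (level -1), 1.5 mg on days 1-10 (level 1) and 2.0 mg on days 1-10 (level 2), and its footnote says "Dose level 1 is the starting dose".

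**The concern.** Table 11 fixes the size of the step in milligrams and ties its stopping rule to a 1 mg dose. Both make sense on a ladder of 2, 1.5 and 1 mg. This protocol's ladder is different: below 1.5 mg on days 1-10 it cuts the number of dosing days and leaves the daily dose alone. Followed literally, Table 11 therefore produces a dose that the protocol prohibits, and its stopping trigger can never be met by a patient dosed within the protocol.

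The more serious case is a patient already on 1.5 mg for days 1-7. After symptomatic retinal toxicity, one table re-exposes that patient to trametinib and the other ends it. Such a patient need not be someone reduced several times. Days 1-7 dosing is level -1 and one of the starting doses listed in Table 4. Section 8.0 allows level -1 to open if level 1 proves too toxic, so it could become the dose for an expansion cohort of 12.

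Safety and tolerability is the primary objective (section 3.1). If sites handle the same event differently, or use a dose outside the escalation schema, that evidence becomes harder to read.

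**Working it through.** The plan states no figure to reproduce here. The check applies Table 11's rule to each dose that Table 4 permits and compares the result with Table 4's next step and with the floor.

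**Inputs**
- Table 11: new daily dose = current daily dose - 0.5 mg; stop only if the current dose is 1 mg.
- Table 4: the ladder described above.
- Floor: 1.5 mg daily (Table 4 title; Dose Reduction Scheme for Trametinib).
- Cycle: 21 days (section 5.2.1.1).
- Assumption: Table 11 names no dosing days, so the patient keeps the current schedule. For the days 1-7 patient, ten-day dosing is also shown.

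**Formula**

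Trametinib per cycle = daily dose x dosing days per cycle.

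| Current dose | Table 11 result | Table 4 result | Table 11 daily dose against floor |
|---|---|---|---|
| 2 mg, days 1-10 | 2.0 - 0.5 = 1.5 mg; 1.5 x 10 = 15 mg per cycle | 1.5 mg, days 1-10; 1.5 x 10 = 15 mg per cycle | meets it |
| 1.5 mg, days 1-10 | 1.5 - 0.5 = 1.0 mg; 1.0 x 10 = 10 mg per cycle | 1.5 mg, days 1-7; 1.5 x 7 = 10.5 mg per cycle | 0.5 mg below |
| 1.5 mg, days 1-7 | 1.5 - 0.5 = 1.0 mg; 1.0 x 7 = 7 mg per cycle (1.0 x 10 = 10 mg if given on days 1-10) | discontinue; 0 mg | 0.5 mg below |

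Two of the three permitted doses conflict, and one of them is the starting level. A patient who begins at 2 mg is unaffected at the first reduction but meets the conflict at the next.

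**Does another rule settle it?** The precedence sentence lets the event tables displace Tables 5 and 6. It does not mention Table 4 or the floor, so it neither authorises Table 11 to override them nor states that they override Table 11. Table 11 itself refers to neither. Tables 7, 9, 12 and 13 also call for a reduced dose level, but none of them attaches a milligram amount. Table 11 is the exception.

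**Can 1 mg be dispensed?** Yes. Section 9.2 lists tablets "equivalent to 0.125 mg, 0.5 mg or 2 mg of trametinib", so two 0.5 mg tablets make 1 mg. This shows only that supply would not prevent the error. The 0.5 mg tablets are also how a 1.5 mg dose can be made up, so their presence does not suggest that 1 mg was intended.

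**The case against.** The best reply is that the protocol already answers the question. The floor is stated without exception, and its second statement comes after all the event tables, where it most naturally limits every one of them. Table 11's main instruction is to drop one dose level, and dose levels are defined in Tables 3 and 4, where 1 mg does not appear. Read together, 1.0 mg is unavailable, and the bracket is a leftover that happens to be right from 2 mg. A site would have to disregard two explicit statements to give 1 mg. At the starting level, even the literal reading delivers slightly less drug per cycle than Table 4.

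Much of this stands. The floor does prohibit 1.0 mg, a careful site could work out the intended action, and no excess exposure arises at the starting level. It does not dispose of the point. The floor says what may not be given; it does not say what to do instead. For the patient on 1.5 mg for days 1-7, Table 11 says restart, its stopping condition is unmet, and the floor forbids the resulting dose. Only Table 4 supplies the answer, and Table 11 does not send the reader there.

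**Conclusion.** The concern holds. Table 11's RPED rule contradicts Table 4 and the 1.5 mg floor for every patient on 1.5 mg.

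At the starting level the consequence is a prohibited daily dose with nearly unchanged exposure. At 1.5 mg on days 1-7 it is continued trametinib against discontinuation. The 7 mg figure for that patient rests on the assumption that the seven-day schedule is kept.

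The rule applies only to patients whose Grade 2-3 RPED improves to Grade 1 or less. The documents give no rate for that event, so no count is offered, and it may be small. Sample size, power and the definition of dose-limiting toxicity are not affected. It should still be corrected, because it is an operative safety instruction that is wrong as written.

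**What to change.** In the Grade 2-3 row of Table 11, replace the restart instruction with: *restart trametinib reduced by one dose level per Table 4, or discontinue in patients already at 1.5 mg D1-D7*.

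The steps then become 2 mg days 1-10 to 1.5 mg days 1-10, 1.5 mg days 1-10 to 1.5 mg days 1-7, and 1.5 mg days 1-7 to discontinuation. No step falls below the floor, and the step from 2 mg is unchanged. The cost is a one-line wording change in a small amendment, with no effect on the design or the analysis.

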Hypophysitis	2-4	Toxicity resolves to Grade 0-1. Therapy with pembrolizumab can be continued while endocrine replacement therapy is instituted	Toxicity does not resolve within 12 weeks of last dose or inability to reduce corticosteroid to 10 mg or less of prednisone or equivalent per day within 12 weeks
Hyperthyroidism	3	Toxicity resolves to Grade 0-1	Toxicity does not resolve within 12 weeks of last dose or inability to reduce corticosteroid to 10 mg or less of prednisone or equivalent per day within 12 weeks
	4	Permanently discontinue	Permanently discontinue
Hypothyroidism		Therapy with pembrolizumab can be continued while thyroid replacement therapy is instituted	Therapy with pembrolizumab can be continued while thyroid replacement therapy is instituted
2 ^b T Infusion		Toxicity resolves to Grade 0-1	Permanently discontinue if toxicity develops despite adequate premedication
Reaction	3-4	Permanently discontinue	Permanently discontinue
Pneumonitis	neumonitis 2 Toxicity resolves to Grade 0-1		Toxicity does not resolve within 12 weeks of last dose or inability to reduce corticosteroid to 10 mg or less of prednisone or equivalent per day within 12 weeks
	3-4	Permanently discontinue	Permanently discontinue
Nephritis or inabi		Toxicity does not resolve within 12 weeks of last dose or inability to reduce corticosteroid to 10 mg or less of prednisone or equivalent per day within 12 weeks	
	3-4	Permanently discontinue	Permanently discontinue
All Other Drug- Related Toxicity ^c	3 or Severe	Toxicity resolves to Grade 0-1	Toxicity does not resolve within 12 weeks of last dose or inability to reduce corticosteroid to 10 mg or less of prednisone or equivalent per day within 12 weeks
	4	Permanently discontinue	Permanently discontinue

Note: Permanently discontinue for any severe or Grade 3 drug-related AE that recurs or any life-threatening event.

In case toxicity does not resolve to Grade 0-1 within 12 weeks after last infusion, trial treatment should be discontinued after consultation with the Sponsor Investigator. Subjects who require corticosteroids to manage drug-related adverse events must be at an equivalent dose of ≤10mg per day of prednisone to resume dosing with pembrolizumab. Furthermore, an inability to reduce

^a For patients with liver metastasis who begin treatment with Grade 2 AST or ALT, if AST or ALT increases by greater than or equal to 50% relative to baseline and lasts for at least 1 week then patients should be discontinued.

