Uncomplicated Diarrhea, ¹ Grade 1 or 2	 Diet: Stop all lactose containing products; eat small meals, BRAT-diet (banana, rice, apples, toast) recommended. Hydration: 8-10 large glasses of clear liquids per day (e.g., Gatorade or broth). Loperamide³: Initially 4 mg, followed by 2 mg every 4 hours or after every unformed stool; maximum 16 mg/day. Continue until diarrhea- free for 12 hours. Diarrhea >24 hours: Loperamide 2 mg every 2 hours; maximum 16 mg/day. Consider adding oral antibiotics. Diarrhea >48 hours: Loperamide 2 mg every 2 hours; maximum 16 mg/day. Add budesonide or other second-line therapies (otreotide, or tincture of opium) and oral antibiotics. 	 Continue trametinib. If diarrhea is grade 2 for > 48h, interrupt trametinib until diarrhea resolves to grade ≤1. Restart trametinib at the same dose level If treatment delay is > 28 days, discontinue trametinib.
Uncomplicated Diarrhea, ¹ Grade 3 or 4 Any Complicated Diarrhea2	 Clinical evaluation mandatory. Loperamide³: Initially 4 mg, followed by 2 mg every 4 hours or after every unformed stool; maximum 16 mg/day. Continue until diarrhea- free for 12 hours. Oral antibiotics and second-line therapies if clinically indicated Hydration: Intravenous fluids if clinically indicated. Antibiotics (oral or intravenous) if clinically indicated. Intervention should be continued until the subject is diarrhea-free for ≥24 hours. Intervention may require hospitalization for subjects at risk of life- threatening complications. 	 Interrupt trametinib and pembrolizumab until diarrhea resolves to ≤ grade 1. Then restart pembrolizumab and trametinib reduced by one dose level.⁴ If 3 dose reductions of study treatment are clinically indicated, permanently discontinue trametinib. If treatment delay is >28 days, discontinue trametinib and pembrolizumab.

¹ Uncomplicated diarrhea defined by the absence of symptoms such as cramping, nausea/vomiting, ≥ grade 2, decreased performance status, pyrexia, sepsis, neutropenia ≥ grade 3, frank bleeding, and/or dehydration requiring intravenous fluid substitution

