² Complicated diarrhea defined by the presence of symptoms such as cramping, nausea/vomiting, ≥ grade 2, decreased performance status, pyrexia, sepsis, neutropenia ≥ grade 3, frank bleeding, and/or dehydration requiring intravenous fluid substitution. Patients with complicated diarrhea should be evaluated for pembrolizumab mediated autoimmune colitis with additional management as specified for pembrolizumab.

³ Loperamide should be made available prior to start of study treatment soloperamide administration can begin at the first signs of diarrhea.

⁴ Escalation of trametinib to previous dose level is allowed after consultation with the study chair and in the absence of another episode of complicated or severe diarrhea in the 4 weeks subsequent to dose reduction.

Table 13. Dose Modification Guidelines and Management for Rash

Rash Severity	Management Guideline	Dose Modification
Grade 1	 Initiate prophylactic and symptomatic treatment measures.¹ Use moderate strength topical steroid.² Reassess after 2 weeks. 	 Continue trametinib. If rash does not recover to baseline within 2 weeks despite best supportive care, reduce trametinib by one dose level.³
Grade 2	 Initiate prophylactic and symptomatic treatment measures.¹ Use moderate strength topical steroid.² Reassess after 2 weeks. 	 Reduce trametinib by one dose level. If rash recovers to ≤ grade 1 within 2 weeks, increase dose to previous dose level. If no recovery to ≤ grade 1 within 2 weeks, interrupt trametinib until recovery to ≤ grade 1. Restart trametinib at reduced dose level.
Grade ≥3	 Use moderate strength topical steroids. Consider oral methyl- prednisolone dose pack.² Consider consulting dermatologist. 	 Interrupt trametinib until rash recovers to ≤ grade 1. Then restart pembrolizumab and trametinib (reduced by one dose level).³ If no recovery to ≤ grade 2 within 4 weeks, permanently discontinue trametinib and pembrolizumab.

Rash prophylaxis is recommended for the first 6 weeks of study treatment.

Moderate-strength topical steroids: Hydrocortisone 2.5% cream or fluticasone priopionate 0.5% cream. Trametinib may be escalated to previous dose level if no rash is evident 4 weeks after restarting study treatment.

Table 14. Pneumonitis Guidelines

CTCAE Grade	Adverse Event Management	Action and Dose Modification

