7.2.4 Evaluating Adverse Events

An investigator who is a qualified physician will evaluate all adverse events according to the NCI Common Terminology for Adverse Events (CTCAE), version 4.0. Any adverse event which

changes CTCAE grade over the course of a given episode will have each change of grade recorded on the adverse event case report forms/worksheets.

All adverse events regardless of CTCAE grade must also be evaluated for seriousness.

 Table 20. Evaluating Adverse Events

An investigator, who is a qualified physician, will evaluate all adverse events as to:

V4.0 CTCAE Grading	Grade 1	Mild; asymptomatic or mid symptoms; clinical or diagnostic observations only; intervention not indicated.					
	Grade 2	Moderate; minimal, local or noninvasive intervention indicated; limiting age-appropriate instrumental ADL.					
	Grade 3	Severe or medically significant but not immediately life-threatening; hospitalization or prolongation or hospitalization indicated; disabling; limiting self-care ADL.					
	Grade 4	Life threatening consequences; urgent intervention indicated.					
	Grade 5	Death related to AE					
Seriousness	A serious a	dverse event is any adverse event occurring at any dose or during any use of Merck product that:					
	†Results in	death; or					
	event as it o	eatening; or places the subject, in the view of the investigator, at immediate risk of death from the occurred (Note: This does not include an adverse event that, had it occurred in a more severe form, caused death.); or					
		a persistent or significant disability/incapacity (substantial disruption of one's ability to rmal life functions); or					
	admission, observation worsened is	or prolongs an existing inpatient hospitalization (hospitalization is defined as an inpatient regardless of length of stay, even if the hospitalization is a precautionary measure for continued at (Note: Hospitalization for an elective procedure to treat a pre-existing condition that has not as not a serious adverse event. A pre-existing condition is a clinical condition that is diagnosed use of a Merck product and is documented in the patient's medical history.); or					
	†Is a congenital anomaly/birth defect (in offspring of subject taking the product regardless of time to diagnosis);or						

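### After drug-related Grade 4 diarrhea, Table 5 ends pembrolizumab but Table 12 restarts it, and the plan does not say clearly which table governs

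*Combined protocol and SAP*

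**What the plan says.** All the dose rules at issue are in Section 5.2.1.2 of the combined protocol and SAP.

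- **Table 5** covers pembrolizumab and drug-related adverse events. For diarrhea/colitis, Grade 2-3 is a hold with restart at Grade 0-1. The entry for Grade 4 is "Permanently discontinue".
- **The note to Table 5** adds: "Permanently discontinue for any severe or Grade 3 drug-related AE that recurs or any life-threatening event". Table 20 in Section 7.2.4 describes Grade 4 as "Life threatening consequences; urgent intervention indicated".
- **The text after Table 6** sets the order of precedence: "Please follow Table 5 and Table 6 for dose modifications unless specified below". It then says that for Grade 3 or higher events "attributed to trametinib both pembrolizumab and trametinib should be simultaneously interrupted with the exceptions shown below".
- **Table 12** follows. One row covers uncomplicated Grade 3 or 4 diarrhea and any complicated diarrhea. Both drugs are interrupted until Grade 1 or less. The next instruction is "Then restart pembrolizumab and trametinib reduced by one dose level". The row's only stop for pembrolizumab is by time: "If treatment delay is >28 days, discontinue trametinib and pembrolizumab".
- **Footnote 2 to Table 12** says: "Patients with complicated diarrhea should be evaluated for pembrolizumab mediated autoimmune colitis with additional management as specified for pembrolizumab".

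**The concern.** An investigator whose patient recovers from drug-related Grade 4 diarrhea has two instructions for pembrolizumab, and they are opposite. Two investigators could follow different tables and both claim compliance. At stake is re-exposure to a checkpoint inhibitor after a life-threatening event for which the protocol's own pembrolizumab table ends treatment, in a trial whose primary objective is safety and tolerability.

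The conflict concerns pembrolizumab only. For trametinib, Table 6 already allows a restart one dose level lower after a Grade 4 event, so Table 12 is consistent with it.

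**Working it through.** The plan states no figure on this point, so the check is a comparison of the texts.

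**Step 1: the two instructions**

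| Drug-related diarrhea | Table 5 (pembrolizumab) | Table 12 (pembrolizumab) |
|---|---|---|
| Grade 3 | Hold, restart at Grade 0-1 | Hold, restart at Grade 1 or less |
| Grade 4 | Permanent stop | Hold, restart at Grade 1 or less |
| Slow recovery | Stop after 12 weeks (Grade 2-3) | Stop after 28 days |

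Grade 3 agrees apart from the time limit. Grade 4 does not agree.

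**Step 2: precedence.** Tables 5 and 6 yield to anything specified below them. Table 12 is below and specifies diarrhea. It also sets a pembrolizumab rule of its own, 28 days against 12 weeks, so it is not merely repeating Table 5. Read literally, its restart displaces the Grade 4 stop.

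**Step 3: is Table 12 limited to diarrhea caused by trametinib?** The titles of Tables 7 to 11 name trametinib; the title of Table 12 does not. The sentence on trametinib-attributed events governs interruption and says nothing about restart. Footnote 2 asks for an evaluation for immune colitis, so the table is in use before the cause is known. No attribution limit is stated.

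**Step 4: does footnote 2 resolve it?** It covers complicated diarrhea, defined by features such as sepsis, fever, bleeding, reduced performance status or dehydration needing intravenous fluids. Nearly all Grade 4 cases would qualify. But the footnote adds evaluation and further management without cancelling the restart in the row. Uncomplicated Grade 4, which the row also names, gets no such pointer.

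**Step 5: does advance approval resolve it?** Table 20 (Section 7.2.4, Rechallenge) requires the sponsor-investigator's prior approval to rechallenge after a serious event that pembrolizumab may have caused. That approval is to follow the protocol's dose modification guidelines, which are the texts in conflict.

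**Step 6: comparison within the plan.** For pneumonitis, Table 14 gives Grade 4 its own row and stops both drugs. A separate Grade 4 instruction is therefore already in use in this section.

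**Step 7: size.** The conflict has effect only if the diarrhea recovers to Grade 1 or less within 28 days; beyond that Table 12 itself stops pembrolizumab. The documents give no rate for such events. For illustration, take an assumed per-patient rate p and the 42 evaluable patients estimated in Section 1.0. The expected number is 42p, and the chance of at least one event is 1 − (1 − p)^42.

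| Assumed p | Expected events | Chance of at least one |
|---|---|---|
| 0.5% | 0.21 | 19% |
| 1% | 0.42 | 34% |
| 2% | 0.84 | 57% |

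The chance reaches 50% at p = 1 − 0.5^(1/42) = 1.6%. With the 12-patient minimum the figure is 1 − 0.5^(1/12) = 5.6%. These numbers give scale only and are no evidence of frequency.

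**The case against.** The strongest defence is that Table 12 manages diarrhea caused by trametinib and Table 5 governs immune colitis. The context supports this. Tables 6 to 11 are trametinib tables, the lead-in sentence speaks of events attributed to trametinib, and the row's treatment is loperamide, fluids and antibiotics without systemic steroids. Section 5.6.2 reserves its steroid-based guidance for events judged related to pembrolizumab. On this view footnote 2 is the link between the two sets of rules. The reading is plausible and may be what the sponsor meant, but the plan does not state it.

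The safeguards also carry weight. Most Grade 4 cases would reach footnote 2. A life-threatening event is a serious adverse event, so the advance-approval rule applies where pembrolizumab may be the cause, whichever table is followed. Section 10.5 adds monthly committee review of new related serious events. These steps make an unconsidered restart unlikely, but they leave the investigator and the approver with two rules.

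A reader might infer more than the documents support:

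- *That Table 12 definitely overrides Table 5.* The precedence sentence allows that reading, but the trametinib-only reading is also open. The text is ambiguous.
- *That pembrolizumab may never resume after a Grade 4 event.* Table 5 allows resumption after hypophysitis and hyperglycemia, and the text after it foresees continuation after some Grade 4 events. For diarrhea/colitis, however, Table 5 is explicit.
- *That recurrent Grade 3 diarrhea has the same problem.* Table 12 has no recurrence rule for pembrolizumab, so the Table 5 note and the recurrence rule after it still apply.

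**Conclusion.** The inconsistency is real and should be corrected. For drug-related Grade 4 diarrhea, Table 5 and its note stop pembrolizumab permanently, Table 12 restarts it, and the precedence sentence can be read in favour of the restart. Footnote 2 and the advance-approval rule reduce the risk without deciding which table governs.

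The reach is small. It covers drug-related Grade 4 diarrhea that recovers within 28 days, and few patients would be affected. That judgement rests on no rate in the documents. The view that nearly all Grade 4 cases would count as complicated is an inference from the footnote definitions.

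It would be wrong to infer that the choice of rule cannot touch dose-limiting toxicity (DLT) assessment. Section 5.4 requires completion of the lead-in and concurrent receipt of both drugs for evaluability. A permanent pembrolizumab stop in the Arm B lead-in can therefore leave a patient unevaluable.

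**What to change.** Split Grade 4 from the combined row of Table 12, or add one sentence to that row, for example:

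> *For Grade 4 drug-related diarrhea/colitis, pembrolizumab is permanently discontinued per Table 5; the restart of pembrolizumab in this row applies only after Grade 3 or lower events.*

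Do not add a new conditional restart route after Grade 4, since that would loosen Table 5. If the sponsor intends Table 12 to allow pembrolizumab after diarrhea caused by trametinib alone, for instance in the Arm A lead-in before any pembrolizumab has been given, the table should say so as an explicit attribution limit.

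This is a short wording amendment with no change to the planned sample size or analysis methods. The cost is that a patient with Grade 4 diarrhea of unclear cause may lose pembrolizumab and, in the Arm B lead-in, may not become DLT-evaluable under Section 5.4.
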